6.1.2.1. Formulation, Packaging, and Labeling

Not Applicable

6.1.2.2. Dosage, Preparation, and Administration

Not Applicable

6.2. Drug Accountability

Not Applicable

6.3. Assessment of Participant Compliance with Investigational Agent

Not Applicable

6.4. Toxicity Prevention and Management

Not Applicable

6.5. Premature Discontinuation of Investigational Agent

Not Applicable

7. Other Medications

7.1. Concomitant Medications

7.1.1. Protocol-mandated

Not Applicable

7.1.2. Other permitted concomitant medications

Not Applicable

7.2. Prophylactic Medications

Not Applicable

7.3. Prohibited Medications

Not Applicable

7.4. Rescue Medications

Not Applicable

8. Study Procedures

8.1. Enrollment/Screening

Screening and enrollment of practice sites, pediatric clinicians, infants, and caregivers will largely take place by collecting data from practice managers or via the EHR pull. Pediatric clinicians and caregivers will provide consent prior to completing any surveys. We have received a waiver of informed consent and written signed

consent for the pediatric clinicians to complete surveys. We have also received a waiver of informed consent and signed consent for caregivers to complete surveys. However, for those caregivers that give permission to link their survey responses with their child's medical records, written signed consent will be obtained.

1. Practice sites will have completed legally-binding engagement agreements with Lurie Children's PPRG prior to study activation. These agreements will describe how EHR data will be accessed, copied, used, and transmitted for research. Once agreements are signed, practices will sign a study-specific Memorandum of Agreement (MOA), which summarizes study procedures and expectations. In addition to the MOA, practices will complete a practice characteristic questionnaire that will document that practice inclusion and exclusion criteria are met.
2. Pediatric clinicians within participating practices will be engaged in the study via practice managers and/or study practice champions once engagement agreements are executed and the Memorandum of Agreements are signed by practice representatives. Practice champions will complete a CRF form ensuring each clinician within participating practice fulfills inclusion/exclusion criteria. The study will be activated and practices are assigned to the respective randomization arms. Prior to survey administration, pediatric clinicians will provide informed consent.
3. Caregivers will have signed a Notice of Privacy agreement (a HIPAA directed agreement) in the practice for which their child is a patient. This document describes how that practice will access, copy, use, and transmit PHI for research purposes. Around the infant's first birthday, the study team will recruit caregivers of all children seen for 4- and/or 6- month WCC (caregivers and infants need to fulfill study inclusion/exclusion criteria) to take the caregiver survey. Caregiver survey will include consent for both 12- and 24-month questionnaires. Procedures for caregiver recruitment will vary across practices and fall into two broad categories: in-person recruitment or remote recruitment, based on practice preferences and policy.

Around the child's first birthday,, an opt-out letter on practice letterhead will be sent to each caregiver whose child was seen at the 4- and/or 6-month WCC. This letter will provide the caregiver an opportunity to opt-out of being contacted for participation in the iREACH study. For those caregivers who do not opt-out, the method for follow-up contact will vary and be based on preference of the practice.

In-person recruitment: This method will use study staff members to recruit caregivers on-site in the pediatric clinics. In coordination with clinic staff, the study staff will approach caregivers arriving for 12-month WCC appointments, collect informed consent, and provide access to the electronic survey instrument.

Remote recruitment:

- If the practices agree to sharing eligible caregiver contact information with the study team, the study team will email, text, and/or call to recruit caregivers. Caregivers have the option to complete the consent, screening questionnaire, and survey online or over the phone. Consent will be obtained and recorded in REDCap prior to administration of surveys.
- For those practices who do not wish to share caregiver contact details, the practices will have a practice representative email and/or call caregivers. Consent will be obtained and recorded in REDCap prior to administration of surveys.

4. Infants seen for a 4- and/or 6-month WCC and who fulfill inclusion/exclusion criteria will be assigned a unique participant number. The caregiver's informed consent will include text allowing for the infant's EHR data to be linked to the caregiver's survey. Once caregivers provide informed consent to link their child's EHR data to the survey, both the survey data and EHR data will be linked to the participant number. If the caregiver wishes to complete the survey but does not want to

link their child's EHR data to the survey, they can indicate this on the consent form and their survey responses will not be linked to their child's EHR record.

8.2. Study Assessments

The assessments for this study are the collection of information through questionnaires (surveys) (Table 8.2.1) and the EHR (Table 8.2.2).

8.2.1. Questionnaires/Surveys

8.2.1.1. Pediatric Clinicians

- Pediatric Clinician Characteristics Questionnaire
- Pediatric Clinician Knowledge, Attitudes, Barriers and Facilitators to Guideline Implementation Questionnaire (KABF)

8.2.1.2. Caregivers

- Caregivers Characteristics Questionnaire (English and Spanish versions)
- Caregivers Feeding, Outcomes, Attitudes, Barriers and Facilitators to Guideline Implementation Questionnaire (FOABF) (English and Spanish versions)

Table 8.1 Data To Be Collected

| Topic | Data | When Collected |
|--|--|--|
| Pediatric Clinician Characteristics | Age, sex, years in practice, type of medical professional, patient volume | After informed consent |
| Pediatric Clinician Knowledge, Attitudes, Barriers, Facilitators to Guideline Implementation (KABF) | Knowledge of PPA Guidelines, attitudes towards guidelines, barriers and facilitators of guideline implementation | Intervention arm: After informed consent, mid-point of observation period & after 1° outcome data collection Control arm: after 1° outcome data collection |
| Caregiver Characteristics | Age, sex, ethnicity, education, income level, geographic location | After informed consent |

| | | |
|---|---|---|
| Caregiver Feeding, Outcomes, Attitudes, Barriers, Facilitators to Guideline Implementation (FOABF) | Peanut introduction practices, attitudes towards PPA Guidelines and barriers/facilitators of guideline implementation | After informed consent |
| Caregiver Report of Child's Adverse Reactions | Any reactions to peanut, and infant's allergy status | After informed consent and when infant is around 24 months old |
| Caregiver Account of Clinician Peanut Recommendations, Testing and Introduction | Information shared with caregiver by pediatric clinician regarding peanut introduction, allergy testing, and/or allergist referrals | After informed consent |
| Caregiver Stress, Quality of Life | Perceived stress and psychosocial outcomes | After informed consent and/or when infant is around 24 months old |
| Child Food Frequency Questionnaire | Detailed peanut and total diet food frequency questionnaire | After informed consent and/or when infant is around 24 months |

8.2.2. EHR Data Extraction

Data collection will take place at both the practice network (e.g., Lurie Community Connect, Peoria area-OSF and Unity Point, Alliance Chicago) or practice level for inclusion in the EHR study database.

Each practice will have an information technology analyst responsible for facilitating data extraction at the practice level. Data from participating practices' EHRs will be extracted on a weekly basis through an automated process established by Lurie Children's Data Coordinating Center team (DCC) and sent to DCC via a secure file transfer protocol (SFTP). Practices will be provided a data dictionary and natural language processing code to identify the appropriate elements and visits/services to extract. DCC will develop Extract Transform Load (ETL) scripts on behalf of the practice network (with the appropriate approvals from the practices). The ETL

scripts will be run weekly so that each week the Lurie Children's DCC data manager will have a complete EHR-based data file for reporting compliance and participation metrics. The weekly file will also be used to identify new providers hired by the practices who may need training in the intervention.

The EHR study database will include data from each of the following types of health care encounters documented in the EHR:

1. 4-month WCC
2. 6-month WCC
3. 9-month WCC
4. 12-month WCC
5. 15-month WCC
6. 18-month WCC
7. 24-month WCC
8. Additional sick visits until 30 months of age
9. Allergy visits until 30 months of age
10. Emergency department visits until 30 months of age

Table 8.2 presents the data elements that will be collected in the EHR study database. Partial PHI including the full date of birth, patient zip code, and date of service will be included.

Table 8.2 EHR Data Elements

| EHR Activities | Data Collected |
|---|--|
| Infant characteristics | Gender, race, ethnicity, date of birth, height and weight over time, patient zip code at 4- month WCC, patient zip code at 6-month WCC, health insurance type at 4-month WCC, health insurance type at 6-month WCC |
| Problem list | Type of problem, date problem entered, date problem resolved |
| Medications list | Medications ordered, order date |
| Primary care visits (well or sick) | Date of service, peanut product introduction recommendation (NLP based), severe eczema (NLP based), eczema ICD-10 code, food allergy ICD-10 codes, date of allergy referral, CDS-specific fields (intervention arm only) |
| Allergy visits | Date of service, peanut product introduction recommendation (NLP based), severe eczema (NLP based), food allergy ICD-10 codes. |
| Peanut testing | Date of test, type of test (peanut sIgE or peanut skin prick test), test result |
| Emergency Department visits | Date of ED visit, food allergy or anaphylaxis ICD-10 codes |

8.2.3. Education

iREACH training (intervention arm) occurs shortly after enrollment. Pediatric clinicians in the intervention arm will be sent a link to complete a web-based video training module covering the PPA Guidelines and use of the iREACH CDS tool. In-person training will be conducted by the study team as requested by the

practice.

8.3. Timeline for Study Activities

Study activities will begin with practice randomization and continue for 18 months of observation.

During the 18-month observation period, all infants that will be seen by pediatric clinicians in participant practices for at least one 4- or 6-month WCC will be considered eligible for EHR data extraction, as long as they (and their caregivers) fulfill inclusion/exclusion criteria. During this period, EHR data will be extracted as described above (Table 8.2). Additional study activities related to the pediatric clinicians that will take place during the same period are described in Table 8.5.1.

For each study infant, information will be obtained through EHR until age 30 months. In addition, activities related to the infant caregivers will take place at 11, 12 and 24 months of the infant's age, as described in Table 8.5.2.

| Table 8.5.1. Schedule of Activities-Practice Sites, Pediatric Clinicians | 18-Month Study Observation Period | | |
|---|--|---------------|------------|
| | Beginning | Middle | End |
| PRACTICES | | | |
| Randomization of Practice Sites | X | | |
| INTERVENTION ARM PEDIATRIC CLINICIANS | | | |
| Pediatric Clinician Informed Consent | X | | |
| Pediatric Clinician Characteristics Questionnaire | X | | |
| Pediatric Clinician Knowledge Attitudes Barriers Facilitators Survey #1 | X | | |
| Pediatric Clinician Knowledge Attitudes Barriers Facilitators Survey #2 | | | X |
| Pediatric Clinician Knowledge Attitudes Barriers Facilitators Survey #3 | | | X |
| CONTROL ARM PEDIATRIC CLINICIANS | | | |
| Obtain Pediatric Clinician Informed Consent | | | X |
| Pediatric Clinician Characteristics Questionnaire | | | X |
| Pediatric Clinician Knowledge Attitudes Barriers Facilitators Survey | | | X |

| Table 8.5.2. Schedule of Activities-Caregivers | Age of Infant | | |
|--|-------------------------|-------------------------|---|
| | Around 12-months | Around 24-months | |
| CAREGIVERS | | | |
| Caregiver Opt-out Letter (if needed based on recruitment method) | | X | |
| Caregiver Informed Consent and Consent to Link Survey with | | X | X |
| Caregiver Characteristics Questionnaire | | X | X |
| Caregiver Feeding, Outcomes Attitudes, Barriers, Facilitators | | X | X |
| Caregiver Account of Clinician Peanut Recommendations, Testing and Introduction Survey | | X | |
| Caregiver Stress, Quality of Life | | X | X |

| | | | |
|--|--|---|---|
| Infant Food Frequency Questionnaire | | X | X |
|--|--|---|---|

9. Mechanistic Assays

Not Applicable

10. Biospecimen Storage

Not Applicable

11. Criteria for Participant and Study Completion and Premature Study Termination

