- d. *A BPA* triggered when the pediatric clinician views peanut sIgE results (for those patients for whom sIgE has been ordered. The BPA will provide the criteria for "positive" results (≥ 0.35 kU/L) and a recommendation to refer to an allergy specialist if results are positive.

Caregiver Handout on How to Introduce Peanut Containing Products: Handout adapted from the NIAID caregiver materials (English and Spanish versions). The handouts were simplified and tested with caregiver groups including low-literacy, underserved families. This handout can be used as part of pediatric clinician counseling and can go home with caregivers as a reminder.

C. Follow-up Prompts at 9- and 12-month WCC: *Smart Texts and Data Elements* that advise the pediatric clinician to ask caregivers and chart whether peanut products have been introduced into their infant's diet. If the caregiver reports that peanut products were introduced, the clinician will be directed to document whether introduction was tolerated. If caregiver reports that peanut products were not introduced, the clinician will be directed to ask the caregiver for reasons why they did not.

Note: For those practices that do not use an Epic-based EHR, Lurie Children's study team will facilitate and work with their informatics teams to implement an iteration of the CDS tool that is compatible with the practice EHR.

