13.4 Analysis Plan

13.4.1 Analysis Populations.

Primary EHR data infant (PEDI) sample: All infants meeting inclusion/exclusion criteria for whom EHR data has been obtained at a 4-month or 6-month WCC in order to assess the primary endpoint of pediatric clinician adherence. Data regarding characteristics of the treating pediatric clinician are not required for an infant to be included in this population.

Secondary EHR data infant (SEDI) samples with pediatric clinician characteristics obtained: All infants meeting inclusion/exclusion criteria for whom EHR data has been obtained at a 4-month or 6-month WCC in order to assess the primary endpoint of pediatric clinician adherence and whose pediatric clinician has consented and completed the characteristics questionnaire information. In addition to characteristics obtained through the characteristics questionnaire information, data on completion of pre-study training for pediatric clinicians in the intervention arm will also be captured.

Exploratory EHR data infant (EEDI) samples

- With allergist adherence obtained (EEDI1): All high-risk infants meeting eligibility criteria who are referred to an allergist for testing and for whom data are obtained regarding the testing that was conducted, the outcome of the allergist testing and the recommendation provided by the allergist as to early introduction of peanut-containing food.
- With caregiver adherence obtained (EEDI2): All infants whose caregivers complete the FOABF and Caregiver Account of Clinician Peanut Recommendations, Testing and Introduction surveys at 12 and/or 24 months.

Pediatric clinician sample: All pediatric clinicians within the intervention group meeting consent and eligibility criteria who complete baseline and at least one follow-up knowledge, attitudes, or barriers and facilitators survey. Those clinicians in the control group will complete one follow-up knowledge, attitudes, or barriers and facilitators survey.

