13.4.2 Primary Analysis of Primary Endpoint(s)

The primary endpoint is the percentage of infants in the PEDI sample within each trial arm whose pediatric clinician adhered to the guidelines regarding peanut introduction. The primary

endpoint concerns peanut introduction recommendation by the treating pediatric clinician only and not additional behavior by the treating allergist or by caregivers.

The primary endpoint will be computed using EHR data from the 4-month and 6-month WCCs as follows:

For low-risk infants:

- Adherence is achieved if the pediatric clinician recommends introduction of peanut products.
- Non-adherence is achieved if the pediatric clinician fails to recommend introduction.

For high-risk infants, adherence is assessed through three routes. A pediatric clinician is adherent if:

- The pediatric clinician does not order an sIgE test and refers the infant to an allergist.
- The pediatric clinician does order an sIgE test, the result is ≤ 0.35 , and the pediatric clinician recommends introduction.
- The pediatric clinician does order an sIgE test, the result is > 0.35 , and the pediatric clinician refers the infant to an allergist.

A pediatric clinician is non-adherent if:

- The pediatric clinician does not order an sIgE test and does not refer the infant to an allergist.
- The pediatric clinician does order an sIgE test, the result is ≤ 0.35 , and the pediatric clinician fails to recommend introduction.
- The pediatric clinician does order an sIgE test, the result is > 0.35 , and the pediatric clinician does not refer the infant to an allergist.

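### The 18-month window opens at randomization with no go-live rule, so infants seen before iREACH is running can dilute the primary comparison

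*Combined protocol and SAP*

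**What the plan says.** **Start of the window.** Section 8.3: "Study activities will begin with practice randomization and continue for 18 months of observation". Table 8.5.1 places randomization, intervention-clinician consent and the first clinician survey at the beginning of that same 18-month period. Section 8.1 puts activation and assignment together: "The study will be activated and practices are assigned to the respective randomization arms".

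**Start of the intervention.** Section 8.2.3: "iREACH training (intervention arm) occurs shortly after enrollment". It is delivered by a link that clinicians must then complete. For practices without an Epic record system, section 6.1.1 says the study team will "work with their informatics teams to implement an iteration of the CDS tool that is compatible with the practice EHR". Section 4.4 names one such network, which uses Centricity. Section 3.2 says control practices receive no additional education and no record-system changes. In contrast, section 13.4.1 says that "data on completion of pre-study training for pediatric clinicians in the intervention arm will also be captured", and 13.4.3 also describes the training as coming before the study.

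**Who is scored, and on what.** Section 8.3: "all infants that will be seen by pediatric clinicians in participant practices for at least one 4- or 6-month WCC will be considered eligible". The primary sample in 13.4.1 (PEDI) takes every eligible infant with record data at a 4- or 6-month visit. Section 13.4.2: "The primary endpoint will be computed using EHR data from the 4-month and 6-month WCCs as follows". None of these carries a go-live or visit-date condition. The supportive analyses in 13.4.3 exclude infants by whether their clinician declined training or the tool. None is defined by calendar time.

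**The concern.** The documents state no roll-in, transition period or go-live date. Two groups of infants follow from the literal rule.

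- **Seen between randomization and go-live.** In the intervention arm these infants receive usual care but count as iREACH outcomes. A clinician trained in month 3 has not declined anything, so the 13.4.3 exclusions leave that clinician's earlier infants in.
- **Entering through a 6-month visit in the first two months.** Their 4-month visit came before randomization. The plan does not say whether a recommendation or referral made then counts, and two analysts could score the same infant differently.

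Both pull the arms together in each co-primary comparison. The secondary peanut-allergy analysis (13.4.4) uses the same sample and inherits the problem.

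**Working it through.** **1. Inputs (13.3, 13.6 and 13.7).** 30 practices, 1:1, so 15 per arm; 17 high-risk and 333 low-risk infants per practice over 18 months; within-practice correlation 0.07; average adherence 0.50; alpha 0.05, two-sided. Stated detectable differences: 18 points (high-risk) and 14 points (low-risk).

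**2. Reproducing the plan's figures.** Effective n per arm = 15m / [1 + (m − 1)(0.07)]. Power = Φ{[d − 1.96√(0.5/n)] / √[(p₁q₁ + p₀q₀)/n]}, with p₁ and p₀ = 0.50 ± d/2 and q = 1 − p.

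- Low-risk: design effect 1 + 332 × 0.07 = 24.24; n = 4,995/24.24 = 206.1. (0.14 − 0.09655)/0.04877 = 0.891, so power is 81.4%.
- High-risk: design effect 1 + 16 × 0.07 = 2.12; n = 255/2.12 = 120.3. (0.18 − 0.12637)/0.06342 = 0.846, so power is 80.1%.

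The stated figures reproduce on the normal approximation. A t reference with 28 degrees of freedom would give 78.3% and 76.9% before any dilution. The rest stays on the plan's scale.

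**3. Infants seen before go-live.** The lag L is an assumption. With even infant flow, the unexposed share is f = L/18 and the observed difference is (1 − f)d. *Kept* leaves these infants in. *Excluded* drops those months from both arms, so m becomes m(1 − f) and d is undiluted.

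| L (months) | f | Low-risk difference | Kept | Excluded | High-risk difference | Kept | Excluded |
|---|---|---|---|---|---|---|---|
| 0 | 0 | 14.0 | 81.4% | 81.4% | 18.0 | 80.1% | 80.1% |
| 1 | 5.6% | 13.2 | 76.8% | 81.3% | 17.0 | 75.4% | 79.1% |
| 2 | 11.1% | 12.4 | 71.6% | 81.2% | 16.0 | 70.1% | 78.0% |
| 3 | 16.7% | 11.7 | 66.0% | 81.1% | 15.0 | 64.5% | 76.7% |

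If every infant attends both visits two months apart, entrants span 18 + 2 = 20 months of births. The share never exposed is then L/20, which is slightly milder: 77.2%, 72.7% and 67.7% low-risk; 75.9%, 71.2% and 66.2% high-risk.

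**4. Four-month visits before randomization.** On the same 20-month span, 2/20 = 10% of infants have a 4-month visit before randomization even if go-live is immediate. They can still meet the tool at 6 months, so 10% is an upper bound on dilution from this source. At that bound, power would be 72.7% low-risk and 71.2% high-risk.

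**5. At the pilot effect (section 1.4).** Low-risk: 75/143 − 44/311 = 52.4% − 14.1% = 38.3 points. Lags of 1, 2 and 3 months leave 36.2, 34.0 and 31.9 points. With a standard error of √(0.5/206.1) = 4.93 points, 31.9/4.93 is about 6.5, so power stays above 99.9%. The high-risk pilot (5/8 against 0/1) is too small to use this way.

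**6. Precision cost of losing 10% of infants.** Variance is proportional to 0.07 + 0.93/m. Low-risk, m from 333 to 299.7: √(0.07310/0.07279) = 1.002. High-risk, m from 17 to 15.3: √(0.13078/0.12471) = 1.024. The standard error rises by about 0.2% and 2.4%.

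**The case against.** **The lag is nowhere stated.** This is correct as to its length. Two places describe training as coming before the study, three of the four listed networks use Epic, and a pilot tool has already run in one practice. But arm-specific training cannot precede assignment, and 8.3 makes assignment the start of the window. No lag at all would require training complete and the tool live at every intervention practice on the day of randomization. The pre-study wording conflicts with 8.2.3 and does not resolve it.

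**Counting every infant from randomization is intention-to-treat.** It is a legitimate choice and a conservative one. Both arms share the window, so type I error is not inflated. But a date fixed before randomization and applied to both arms keeps the randomized comparison just as well.

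**The power loss is computed at the detectable difference.** Any dilution there falls towards or below 80% by construction, and 13.7 does not present 14 or 18 points as the expected effect. This stands, which is why the pilot calculation is shown beside it.

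**Stronger readings that a reader might infer.** One is that the plan does score actions taken before randomization. It does not say so. Section 8.3 ties eligibility to visits in the window and says data are extracted during that period, while 13.4.2 sets no date limit; the rule is unspecified. Another is that the slowest network suffers most, but the documents give no build time for any network. A third is that the primary cohort should be limited to infants reaching 4 months after go-live. That would drop infants with a fully exposed 6-month visit, whom section 4.2 makes eligible.

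**Conclusion.** The concern holds as a gap in the start rule. As written, the window opens before the intervention can be fully in place, and nothing in the sample definition, the endpoint rule or the sensitivity analyses separates infants seen before go-live. The harm is an attenuated odds ratio and reduced power in both co-primary comparisons. It is not a false-positive risk.

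The size depends on a lag the documents do not give, and on even infant flow. At 1 to 3 months, the loss at the plan's detectable differences is about 5 to 15 percentage points of power low-risk and 5 to 16 high-risk. If the low-risk effect is near the pilot's, the conclusion would survive and only the estimate would be too small. The high-risk comparison has no comparable reassurance. Four-month visits before randomization add at most 10% dilution, and only if the plan means to count them.

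**What to change.** **Section 8.3.** Start the 18-month window at a calendar Day 0 for each network, fixed before randomization and planned to follow training release and tool activation. Apply the same date to that network's control practices. Record the actual activation date in each intervention practice. Infants seen after Day 0 but before a late activation stay in the primary analysis.

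**Sections 13.4.1 and 13.4.2.** Keep infants with at least one 4- or 6-month visit on or after Day 0. Count only visits on or after Day 0 towards adherence, in both arms.

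**Section 13.4.3.** Add two sensitivity analyses: the current set (any visit since randomization), and infants who reach 4 months of age on or after Day 0.

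**Wording.** Reconcile the training time in 8.2.3 with the pre-study descriptions in 13.4.1 and 13.4.3.

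**Cost.** Dates of birth and service are already collected (section 8.2.2), so no new infant data are needed. The calendar window slides by the lag. If it is not extended, excluding 3 months would leave power at 81.1% low-risk and 76.7% high-risk. One side effect is that a recommendation made only at a 4-month visit before Day 0 no longer counts, so some infants are scored on one visit. The date rule is the same in both arms, and the second sensitivity analysis shows whether it matters.
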